**Comparison between single shot peripheral nerve block and continuous infusion via a On-Q
Pump: a randomized prospective control trial**

Principal Investigator: [name]

Co-investigators:

[name]

[name].

[name], BS

Department of Orthopaedic Surgery

NYU-Hospital for Joint Diseases

[name]

[name]

Brief Summary

Peripheral nerve blocks have been well studied in the literature with generally good results for controlling post operative pain following orthopaedic surgery. Regional anesthesia has many benefits. It provides excellent intraoperative anesthesia and muscle relaxation as well as analgesia that continues into the post-operative period. These regional blocks are also effective in controlling pain in the immediate post-operative period. However, as the block wears off, patients begin experiencing increased pain. Compared to patients treated without regional blocks, these patients will often experience a "rebound pain"--pain occurring 12-24 hours after surgery that is subjectively worse than that in patients treated without regional blocks. Therefore, we propose to use a continuous infusion of anesthetic in order to provide sustained pain control post-operatively. Preoperatively, patients will be randomized into a single shot peripheral nerve block versus a continuous infusion of peripheral nerve block. Post-operatively, pain will be assessed using the Visual Analogue Scale (1-100) prior to being discharged from PACU. Time to discharge and amount of pain medication taken will be recorded. Patients will be contacted at certain time intervals postoperatively to assess their pain scale and pain medication intake. Patients will be seen for routine post-operative follow-up visits where they will be assessed for satisfaction, pain, residual neurological symptoms, and signs of infection.

Purpose

The purpose of this randomized prospective study will be to compare post-operative pain control after extremity fracture fixation surgery between patients who receive single shot versus continuous peripheral nerve blocks.

Scientific or Scholarly Rationale

Peripheral nerve blocks have been well studied in the literature with generally good results for controlling post operative pain following orthopaedic surgery ¹⁻⁴. Regional anesthesia has many benefits. It provides excellent intraoperative anesthesia and muscle relaxation as well as analgesia that continues into the post-operative period. Airway manipulations are avoided, post-operative nausea and vomiting are diminished, post-anesthesia care unit stay are shortened, and fewer nursing interventions in the post-anesthesia care unit are required⁵⁻⁶.

Patients who have operative fixation of extremity fractures (ankle, wrist, forearm) are typically ambulatory patients. However, many become hospitalized overnight secondary to inadequate pain control, increasing hospital costs. Goldstein et al. showed that patients who underwent popliteal blocks after ankle fracture fixation demonstrated significantly better pain control immediately postoperatively⁷. The need for overnight hospitalization secondary to pain is decreased, as are nonsurgical operating room times.

Despite the success of regional anesthesia, a phenomenon known as "rebound pain" has been shown to occur as the original block wears off⁷⁻⁹. Patients with blocks will experience significantly increased pain compared to those without blocks approximately 12-24 hours after surgery. This can be controlled with early narcotic administration but can be a source of significant discomfort to a patient if not recognized

and treated in time. A few studies have shown that continuous infusions of various numbing agents are efficacious in prolonged pain control, even in the ambulatory setting¹⁰⁻¹². Nevertheless, no studies have thus performed a randomized prospective control trial studying the efficacy of continuous infusion therapy on pain control following extremity fracture surgery.

Aims

1. To determine the effectiveness of continuously infused regional anesthetic for pain control in extremity fracture surgery
2. To determine the effect of rebound pain on patient satisfaction of surgery

Description of study and study procedure

Consent

All patients being treated with open reduction internal fixation for foot, ankle, tibia, elbow, forearm and wrist fractures at New York University Medical Center, NYU-Hospital for Joint Diseases will be asked to participate in this study. At the patients preoperative office visit, they will be asked to participate in the study and provided a copy of the consent form at that time which they can take home with them. All questions will be answered and they will be asked verbally if they will consent to being a part of the study. Patients will then have the opportunity to either sign the written consent forms or wait till the surgical date to think about the study and any additional questions they may have. At the time of surgery, patients will be consented for surgery. If the patient did not give written consent at the preoperative visit, they will be asked if they have any questions about the study. All questions will again be answered. They will then be asked verbally if they are willing to participate in the study, if they respond yes, then written consent will be obtained at that time.

Randomization

Patients will then be randomized (using an online randomizer, similar to a flip of a coin) to one of two anesthetic protocols: regional block with single dose of anesthetic versus regional block with continuous infusion using an OnQ pump. If for some reason, the anesthesiologist feels that a patient would benefit from one type of anesthesia over another, the patient will be removed from the study and given that type of anesthesia.

Intervention

Patients will be randomized to one of two anesthetic protocols: general anesthesia/sedation with a single shot, peripheral nerve block versus general anesthesia/sedation with a continuous, peripheral nerve block.

All anesthesia will be provided by an attending anesthesiologist with or without an anesthesiology resident/CRNA. Patients will have standard ASA monitors placed (pulse oximeter, blood pressure, EKG) and an intravenous line started. Sedation will be given using a combination of midazolam (1-4 mg) and fentanyl (25-100 mcg). Patients in both groups will receive an ultrasound-guided peripheral nerve block. The block will be either an infraclavicular brachial plexus block or a popliteal nerve block, depending on

the location of the fracture. The appropriate region will be prepped with a chlorohexidine solution on the appropriate surgical side and the appropriate site will be visualized under ultrasound. For the group receiving a single shot block, a 22 gauge, 3.5 inch needle will be used and 20cc of 2% lidocaine with 1:200,000 epinephrine + 20 cc of 0.5% bupivacaine with 1:300,000 epinephrine will be injected around the nerve after confirming negative aspiration every 5 cc. For those receiving a continuous infusion, a 17 gauge Tuohy needle will be used and 20cc of 2% lidocaine with epinephrine + 20 cc of 0.5% bupivacaine with 1:300,000 epinephrine will be injected around the nerve after confirming negative aspiration every 5cc. Once the injection is complete, an indwelling catheter will be placed with its tip location confirmed and then secured at the skin.

After placement of the regional block, general anesthesia/sedation will be administered and maintained at the discretion of the anesthesiologist. Induction of anesthesia will involve IV propofol (2mg/kg) and fentanyl (1-2mcg/kg). Neuromuscular blockade will be used at the discretion of the anesthesiologist and will be reversed appropriately. Anesthetic maintenance will involve inhalational agents, IV agents, air, and oxygen. Fentanyl will be the only intraoperative analgesic used and will be dosed as determined by the anesthesiologist.

After completion of the surgery, patients will be taken to the PACU where those with continuous catheters will have an OnQ pump attached to it. The patient will begin receiving a continuous infusion of 0.2% ropivacaine through the catheter at a rate of 8 cc/hr. The patient will be discharged home with the catheter for 48 hours. The study participant will self-discontinue the catheter in 2 days. This involves removing the tegaderm dressing and gently pulling the catheter out from under the skin. A bandage may then be applied. [name], our anesthesiology RN, will be available via phone to answer any questions study participants may have regarding discontinuation of the catheter. Breakthrough pain while in the PACU will be treated with IV fentanyl and PO Percocet as needed.

Postoperatively, all patients will be discharged home with a prescription for Percocet 5/325 with instructions to take 1-2 tabs every 4-6hrs as needed for pain.

Data collection

Location and type of surgical procedure, duration of procedure, and duration of intravenous sedation will also be recorded. Total time in the operating room will also be noted. Time admitted to PACU, time clinically ready for discharge, time actually discharge, PACU medications for nausea/vomiting and PACU meds for pain will all be recorded prior to discharge.

Post-operative pain will be assessed using the Visual Analogue Scale (0-100) prior to being discharged from PACU. Time to discharge and amount of pain medication taken in the PACU will be recorded.

Patients will be contacted 8 hours, 12 hours, 24 hours, 48 hours and 72hrs after surgery by the operative surgeon or research coordinator to assess their pain scale and pain medication intake. Patients will be seen for routine post-operative follow-up visits at two, six, twelve, twenty-four, and fifty-two weeks. At these times, patients will be assessed for pain, residual neurological symptoms, and signs of infection. Patients will also be asked if they were satisfied with their postoperative pain control. Total duration of study will be fifty-two weeks. Data collection documents will be distributed to the patients at time of surgery to assist in patient understanding.

Inclusion criteria

1. Patients at least 18 years old.
2. Male or Female
3. All racial and ethnic groups
4. Fractures and fracture/dislocations of the foot, ankle, tibia, fibula, elbow, forearm, wrist and hand
5. Patients who opt for surgical treatment of their fractures.
6. Patients who consent to be randomized.
7. Patients who are willing to follow-up for a minimum of 52 weeks.

Exclusion criteria

1. Patients younger than 18 years old.
2. Patients who are on chronic opioids
3. Patients who abuse opioids
4. Patients who are unwilling to follow-up for a minimum of 52 weeks.
5. Neurologic condition that could interfere with pain sensation

Characteristics of the Research Population

1. **Total number of subjects:** 100 subjects
2. **Gender:** Male or Female
3. **Racial and Ethnic Origins:** All are included

Study payments/cost:

Study participants will not incur any additional costs or payments as a result of this study. Any additional costs will be absorbed by the NYU Departments of Orthopaedics and Anesthesia

Potential Risks and Discomforts:

The research-related complications associated with regional block include, but are not limited to, intravascular injection, local anesthetic toxicity, hematoma formation around insertion site, infection around injection site, permanent or temporary nerve injury, and allergic reactions to the medication injected.

The research-related complications associated with the On-Q pump include, but are not limited to, site infection, superficial nerve injury, and local anesthetic toxicity. There may be additional risk of injury in the On-Q pump Group, if participants resume regular activities, prematurely, while free of pain.

There may be unknown risks/discomforts involved. Study staff will update all patients in a timely way on any new information that may affect the patients' health, welfare, or decision to remain in the study. If the patients have any questions or sustain any injury during the course of the research or experience any adverse reaction to one of the surgical treatments they will be informed during the process of obtaining informed consent that they should contact the Principal Investigator [name] at the following [contact].

In addition, if there is any Adverse Event that occurs during the study, then the Principal Investigator will make the IRB aware of this. The Principal Investigator will submit a Reportable Events Form for all reportable information to the IRB within 5 working days from when the Principal Investigator learns of the event or new information.

Potential Benefits: The patients are not likely to receive any direct benefit from their participation in this study aside from possible increased pain relief after operative fixation of their fracture. However, the patients' participation may help the investigators better understand the best post-operative pain protocol for extremity fracture fixation. In addition, the patients' participation may help the investigators better understand if there is any prolonged benefit to one post-operative treatment over the other, which could thereby give orthopaedic surgeons conclusive evidence of the best post-operative pain protocol for operative fractures about the forearm and wrist that could also translate into better patient satisfaction.

Data Monitoring Plan:

1. Types of data or events:
 - a. Intravascular injection
 - b. local anesthetic toxicity
 - c. hematoma formation
 - d. Infection
 - e. Neurologic injury
 - f. Allergic reaction
2. Responsibilities and roles for gathering, evaluating and monitoring the data:
 - a. All data (including details about adverse/unexpected events) will be collected by the operative team or research coordinator at specific time points: 8hrs post-op, 24hr, 48hr, 72hrs, 2wks, 6wks, 12wks, 24wks and 52wks and reported to the research coordinator using standard templated data collection forms. All patients will be told to call [name] at [contact] to report adverse reactions during the study.
 - b. All data will be verified by the research team and coordinator for accuracy and compliance with the protocol at each time point as designated above.
3. Information about the monitoring entity:
 - a. Principle investigator [name], [name], and [name] comprise the monitoring entity.
4. Reporting Adverse events and Unanticipated problems to the monitoring entity:
 - a. The Principal Investigator will submit a Reportable Events Form for all reportable information to the IRB within 5 working days from when the Principal Investigator learns of the event or new information.
5. Assessments:
 - a. The Monitoring entity will review data monthly and assess the data for unanticipated problems involving risks to participants.
6. Criteria for Action:
 - a. Specific triggers for action include any event that is deemed to be a risk to life or limb.
7. Procedure for communicating:
 - a. The Principal Investigator will submit a Reportable Events Form for all reportable information to the IRB within 5 working days from when the Principal Investigator learns of the event or new information.

Data Storage and Confidentiality: All patients will be de-identified and given a code. Information linking the linkage codes to the participants' names, social security numbers and medical record numbers will be stored in a secure location separate from the medical information. Access to the information linking the linkage codes with participant identifiers shall be documented. The patient's informed consent will be obtained in one of the exam rooms in the private office.

Participant medical information will be stored electronically within a password protected spreadsheet available only to the PI, co-investigators, and research staff as necessary for data analysis. The names, social security numbers, and medical record numbers of the study participants will be deleted from their stored medical information and replaced with a linkage code. Access to participant medical information contained within the registry will be restricted.

Protection Against Risk: All procedures will be performed as outlined above. After the procedure pt will be contacted 6-8 hours after surgery and at 24 hours, 48 hours and 72hours after surgery by the operative surgeon or research coordinator to assess their pain scale and pain medication intake. Patients will be seen for routine post-operative follow-up visits at two, six, twelve, twenty-four, and fifty-two weeks. At these times, patients will be assessed for pain, residual neurological symptoms, and signs of infection, and starting at the six week time point, patient's functional status will be assessed using the Disability of the Arm, Shoulder and Hand (DASH) and SMFA scores, both are widely accepted and validated functional measures.

Method of Subject Identification and Recruitment: All patients seen in the outpatient office, who fit the inclusion criteria will be asked to participate in the study.

Subject/Representative Comprehension: None

Debriefing Procedures: All patients will have regular follow-up at which point, all questions regarding the study can be answered.

Documentation of Consent: A copy of the signed consent form will be securely kept for our records.

Statistical analysis plan:

A preoperative power analysis was performed. On a VAS scaled from 1-100, assuming a standard deviation of 20, the number needed to detect a 10 point change in VAS was 38. Assuming a drop out rate of 20%, we will require 50 patients in each group to determine significance. The primary end points of the study for Visual Analog Score will be assessed using two-group t-tests (Mann-Whitney U test where appropriate). Amount of pain medication utilized post operatively will be assessed using Student t-tests. Residual neurological symptoms and signs of infection will be reported as descriptive statistics. Descriptive statistics will be reported as means +/- SD for continuous variables and as frequencies and percentages for categorical variables.

References

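### The plan lets the anesthesiologist remove patients after randomization, does not require that judgement before the arm is known, and does not keep removed patients in the analysis

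*Combined protocol and SAP*

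**What the plan says.** The Consent section ends with written consent. The Randomization section then opens: "Patients will then be randomized (using an online randomizer, similar to a flip of a coin", followed by the two techniques. Its next sentence sets the removal rule. The trigger is worded as "If for some reason, the anesthesiologist feels that a patient would benefit from one type of anesthesia over another". The consequence laid down for such a patient is that "the patient will be removed from the study and given that type of anesthesia". No criteria, time limit or allocation-blind condition is attached, and the judgement is not among the five listed exclusion criteria.

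The Intervention section has an attending anesthesiologist provide all anesthesia, with visibly different equipment by arm: "For the group receiving a single shot block, a 22 gauge, 3.5 inch needle will be used", whereas for the continuous block "a 17 gauge Tuohy needle will be used" and a catheter is left in place.

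On analysis, the Statistical analysis plan says "The primary end points of the study for Visual Analog Score will be assessed using two-group t-tests (Mann-Whitney U test where appropriate". On numbers it says "Assuming a drop out rate of 20%, we will require 50 patients in each group to determine significance". It names no analysis population and has no intention-to-treat statement. It does not provide for following, analysing or reporting removed patients.

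**The concern.** Randomization protects the comparison only if who stays in does not depend on the arm drawn. An anesthesiologist who prefers one technique for a patient has little reason to act when that technique has been drawn, and good reason to act when it has not. If the removal option is used in that way, each arm loses a different kind of patient.

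The direction cannot be read from the plan. If patients expected to have much pain leave the single-shot arm, that arm looks better and a true pump benefit is partly hidden. If they leave the pump arm, the pump looks better than it is. Removed patients contribute no outcome data, so the planned two-group tests can neither reveal nor correct the imbalance. The 20% allowance covers lost numbers, not lost comparability.

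**Working it through.** **1. Is there a safeguard in the text?**

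| Safeguard | What the documents provide |
|---|---|
| Judgement recorded before allocation | None. The rule follows the randomization sentence and gives no time. |
| Concealed allocation | None described, only an online randomizer. |
| Criteria for the judgement | None; any reason suffices. |
| End of the removal option before the arm is known | None. The operator knows the arm at the latest when the block is placed. |
| Follow-up of removed patients | None. |
| Analysis as assigned | None; no analysis set is named. |

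**2. The plan's own figures.** For a 10-point difference with SD 20, two-sided 5% (assumed; the plan states neither alpha nor power) and 80% power, n per arm = 2(1.96 + 0.84)² × 20²/10² ≈ 63. The plan's 38 is not reproduced. That is a separate matter and this point does not depend on it. The dropout step is close: 38/0.8 = 47.5, so 48, against the stated 50. With 50 per arm and 20% dropout, 40 per arm remain, and t-test power for 10 points is 59.8%. That is the baseline below.

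**3. Size of the possible bias (illustration).** From the Statistical analysis plan: SD 20, 50 per arm, 20% dropout. Assumed: k of 50 patients removed; the judgement correlates ρ = 0.3 to 0.5 with the VAS the patient would report; removals come on top of dropout.

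If the top fraction f = k/50 by judgement leaves one arm, that arm's mean falls by about ρ × SD × φ(z)/(1 − f), where z is the upper-f normal point and φ the normal density. For k = 5: f = 0.10, φ(z) = 0.1755, and 0.1755/0.90 = 0.195. The shift is 0.3 × 20 × 0.195 = 1.17 to 0.5 × 20 × 0.195 = 1.95 points. For k = 10: 0.2800/0.80 = 0.350, giving 2.1 to 3.5 points.

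Power check for k = 5, ρ = 0.5: 36 and 40 patients remain, SE = 20√(1/36 + 1/40) = 4.595, and power ≈ Φ((10 − 1.95)/4.595 − 1.96) = 42%.

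Simulation (40,000 trials per setting, pooled t-test, two-sided 5%) gives, as ranges over ρ = 0.3 to 0.5:

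| Pattern | 2 of 50 | 5 of 50 | 10 of 50 |
|---|---|---|---|
| Same removal in both arms: shift | about 0 | about 0 | about 0 |
| Same removal in both arms: power | 58-59% | 56-58% | 52-54% |
| Highest expected pain, single-shot only: shift toward single-shot | 0.5-0.9 | 1.2-1.9 | 2.1-3.4 |
| Same pattern: type I error | 5-6% | 6-7% | 7-11% |
| Same pattern: power for a true 10-point pump benefit | 52-55% | 42-48% | 29-38% |
| Highest expected pain, pump only: false conclusions favouring the pump (2.5% nominal) | 3-4% | 4-6% | 6-11% |

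With no removals, type I error is 5.1% and power 59.7%. With ρ = 0 there is no bias.

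**The case against.** The strongest reply is that the order of events is inferred. The clause gives no time, and a consented patient could be removed before allocation. The trigger is a preference for either technique, whichever arm was drawn, so read literally the rule is neutral between arms. Different needles show only that the operator eventually knows the arm, as in any open comparison of techniques. This is right as far as it goes: the documents do not show that biased removal will happen. But nothing requires the neutral reading, and the clause places removal after randomization without restricting it.

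The magnitude can also be challenged. The removal rate, the correlation, one-arm removal and strict selection of the highest-ranked patients are all assumed. At a correlation of 0.1 the shifts are only about 0.2, 0.4 and 0.7 points for 2, 5 and 10 of 50, with type I error about 5%. If removed patients are counted inside the 20% dropout, neutral removal costs no power (about 61-64%). Both points stand. The second does not touch the one-arm bias.

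Finally, the Purpose describes the comparison as "between patients who receive single shot versus continuous peripheral nerve blocks". That is ordinary descriptive wording and weak evidence of an as-treated analysis. The conclusion does not need it: the absence of any stated analysis set is enough.

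**Conclusion.** The concern holds: the plan contains a rule that permits exclusion of randomized patients in a way that can depend on the arm drawn, and nothing elsewhere closes the gap. That conclusion rests on the text alone. The size is not knowable from the documents. It is nil if removal ignores the arm or the judgement does not predict pain, and small at 2 of 50. Under the stated assumptions it becomes material from about 5 of 50 in one arm: 1.2 to 1.9 points against a 10-point target. The direction is unknown. This should be fixed before enrolment, because removed patients' outcomes cannot be recovered afterwards.

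**What to change.** Make the existing judgement an eligibility step. Suggested wording: *Before the allocation is obtained, the anesthesiologist's judgement on whether one technique is favoured is recorded. If one is favoured, the patient is not randomized. The allocation stays concealed until this is recorded.*

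For patients already randomized, replace removal from the study with: *Every randomized patient stays in follow-up and is analysed in the assigned group, whatever technique was given.* Name that as the primary analysis set in the Statistical analysis plan, and report departures by arm with reasons. The rule on which technique a patient is given does not change.

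Cost: wording, and the order of two steps. Patients screened out must be replaced to reach 100. Departures kept in the analysis dilute the effect. If k of 50 single-shot patients receive the pump, a true 10 points is estimated as 10 × (1 − k/50), or 9.6, 9.0 and 8.0 for k = 2, 5 and 10, with power about 56-57%, 51-52% and 43-44% and type I error still about 5%. That is less power than neutral removal would leave (58-59%, 56-58%, 52-54%), but no worse than one-sided removal from single-shot. The loss is the price of protection against bias, and judging suitability first should keep departures few.

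### Frequent pain and opioid collection ends at 72 h, about 24 h after planned catheter removal, so a 72-hour opioid total or an early VAS comparison could count delay as saving

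*Combined protocol and SAP*

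**What the plan says.** - **Early contacts (Data collection).** "Patients will be contacted 8 hours, 12 hours, 24 hours, 48 hours and 72hrs after surgery", in each case "to assess their pain scale and pain medication intake". Pain medication given in the PACU is recorded separately.
- **Later visits (Data collection).** Clinic visits follow at 2, 6, 12, 24 and 52 weeks. "At these times, patients will be assessed for pain, residual neurological symptoms, and signs of infection"; satisfaction with pain control is also asked. Medication intake is not on the list. Protection Against Risk repeats the visits and adds functional scores from six weeks, again without medication.
- **Data Monitoring Plan.** This says in general terms that all data are gathered at "8hrs post-op, 24hr, 48hr, 72hrs, 2wks, 6wks, 12wks, 24wks and 52wks". It does not name medication.
- **Infusion (Intervention).** "The patient will be discharged home with the catheter for 48 hours". The pump is connected in the PACU, and the patient removes the catheter at two days.
- **Rebound (Scientific or Scholarly Rationale).** "Patients with blocks will experience significantly increased pain compared to those without blocks approximately 12-24 hours after surgery". The text links this to the block wearing off.
- **Analysis (Statistical analysis plan).** "Amount of pain medication utilized post operatively will be assessed using Student t-tests". No window is given for that amount, and no time point for the primary VAS comparison.

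**The concern.** Both arms are followed on one clock that starts at surgery, but their blocks end at different times. By 72 h the single-shot arm has been through its rebound window and had two further contacts, at 48 and 72 h. The pump arm has had one contact since planned removal, because the 48 h contact falls at about the end of the infusion. Nothing is then scheduled until two weeks, which is too late to show what happened on days 3 to 5.

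The case for the pump is that it avoids rebound pain, and Aim 1 asks whether it is effective. An infusion that lowers pain and opioid use differs from one that moves the same pain and tablets to a later day. A summary that stops about a day after the infusion can confuse the two, and tablets taken after 72 h cannot be recovered later if nobody asked about them.

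**Working it through.** The plan gives no figure on this point to reproduce. The inputs are the contact times, the 48 h catheter period, the 12–24 h rebound window and the home prescription (one to two tablets every four to six hours, under Intervention).

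**1. Observation after block end, up to 72 h**
- Pump arm: 72 − 48 = about 24 h. This assumes that the 48 h clock starts close to the end of surgery and that the block ends at removal. No offset time is stated.
- Single-shot arm: 72 − 24 = 48 h to 72 − 12 = 60 h, with the rebound window as proxy for block end.
- Shortfall in the pump arm: 48 − 24 = 24 h to 60 − 24 = 36 h.
- Time at which the pump arm would have equal observation: 48 + 48 = 96 h to 48 + 60 = 108 h after surgery.

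**2. Contacts**

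On the Data collection schedule, the single-shot rebound window has contacts at 12 and 24 h. The first day after catheter removal has one, at 72 h. The Data Monitoring Plan and Protection Against Risk omit the 12 h contact; on those schedules each arm has one contact in the corresponding period. On every schedule the single-shot arm still has contacts at 48 and 72 h after its rebound window, and the pump arm has nothing between 72 h and two weeks.

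**3. How many tablets delay alone could hide by 72 h (assumed models)**
- The prescription, if taken regularly, gives 24/6 × 1 = 4 to 24/4 × 2 = 12 tablets a day.
- Pure delay, constant use: shortfall × rate = 24 h × 4/24 = 4 tablets to 36 h × 12/24 = 18 tablets.
- Pure delay, use decaying after block end: with starting rate r per hour, time constant τ and single-shot block end w, the gap is rτ[exp(−24/τ) − exp(−(72 − w)/τ)]. For r = 1/6 to 1/2, τ = 24 to 96 h and w = 12 to 24 h, this runs from 0.9 to 11.7, or about 1 to 12 tablets.
- Need dependent only on time since surgery: 0. Any saving seen is then real.

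**4. What a total hides and intervals show**

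This illustration assumes no tablets under block, then 8, 6 and 4 in successive 24 h periods, with block end at 18 h (single-shot) and 48 h (pump). Use is the same in both arms by construction.

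| Interval | Single-shot | Pump |
|---|---|---|
| 0–24 h | 6 × 8/24 = 2 | 0 |
| 24–48 h | 18 × 8/24 + 6 × 6/24 = 7.5 | 0 |
| 48–72 h | 18 × 6/24 + 6 × 4/24 = 5.5 | 8 |
| **0–72 h total** | **15** | **8** |
| After 72 h | 3 | 6 + 4 = 10 |
| **Overall** | **18** | **18** |

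The 72 h total shows 7 fewer tablets when the true saving is 0. The 48–72 h row reverses (5.5 against 8), so interval data reveal the shift. Only a count after 72 h shows that the whole difference disappears. In this example all tablets are taken by 48 + 72 = 120 h, well before two weeks.

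**The case against.** The strongest reply is that comparing randomised arms on a common clock from surgery is legitimate, and that sustained early pain control is the stated goal. That stands: less pain at 24 or 48 h is a real benefit at that time. It does not support a claim of less pain or opioid overall.

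A reader might also infer several stronger things that the documents do not support:
- **That pain follow-up stops at 72 h.** It does not. Pain is assessed from two weeks to 52 weeks. The gap lies between 72 h and two weeks.
- **That rebound after the pump is missed.** The 72 h contact can cover the first day off the pump, including its tablets, and the documents do not say when rebound would follow removal. The weakness is a single contact.
- **That the comparison must favour the pump.** At 72 h the pump arm is nearer its block end, so a VAS taken then could count against it.
- **That 72 h data can never reveal delay.** Analysed per interval, they can show a reversal, as in the table. A cumulative total hides it.
- **That the example's 7 tablets out of 15 (47%) estimates the bias.** The rates and the equal overall use are assumed, and other assumptions give anything from 0 to about 18 tablets.

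It can be argued that the Data Monitoring Plan's general statement about all data covers medication at later visits. It may be meant that way, but it names no medication item, and neither list of visit assessments includes one.

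**Conclusion.** The concern holds in a limited form. Frequent collection ends about 24 h after planned catheter removal, against about 48–60 h after the single-shot rebound window. The pump arm has one contact after removal and then none until two weeks, and medication intake is not named at any visit after 72 h. A cumulative 0–72 h opioid total, or a VAS comparison at 24 or 48 h, could therefore present postponed pain and tablets as a saving.

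The direction is not fixed, because it depends on a VAS time point and an opioid window that the SAP does not name. Nor is the size known: 0 tablets if need follows time since surgery alone, up to about 18 under pure delay at the upper prescribed rate. These figures rest on the rebound window as a proxy for block end, on removal at about 48 h after surgery, and on the assumed patterns of use.

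**What to change.** The changes concern measurement and reporting only.

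1. At the existing two-week visit, record total Percocet tablets used since surgery (dispensed minus remaining, plus refills). Report the surgery-to-two-week total by arm beside the 0–72 h total.
2. Report opioid use for 0–24, 24–48 and 48–72 h as well as the total, so that a shift to later use is visible. This requires each contact to record intake since the previous one.
3. Describe 0–72 h results as covering the infusion and about 24 h after it, and do not claim an overall opioid reduction unless the two-week total agrees.

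Optional: one short call at about 96–108 h in both arms, which would equalise observation after block end. An extra contact before 72 h would not do that.

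The cost is one question and a tablet count at a scheduled visit, some SAP wording, and one call per patient if the option is taken. The two-week total will be noisier than the 72 h total, which is a reason to report it alongside rather than make it the main comparison. The apparent saving may shrink. These steps do not supply the missing primary VAS time point, which the SAP still needs to name.
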